#### Amendment rationale

Amendment 05 address feedback obtained from the PEI and the IEC on protocol version 7.0. Some changes were also implemented to align data collection and reporting in this trial with the data collection and reporting in other trials with BNT162 vaccines candidates (to facilitate data merging).

This amendment will be issued after some of the planned trial subjects have already been enrolled into the trial.

#### 10.10.6 Protocol amendment no. 06

#### Amendment rationale

Protocol amendment 6.0 implemented three additional cohorts (Cohorts 11, 12, and 13) comprising up to additional 150 trial subjects aged from 18 to 85 years receiving BNT162b2 only.

BNT162b2 has entered a Phase II/III evaluation of efficacy, with the intent to support an application for marketing authorization. The dosing regimen under investigation is two  $30 \ \mu g$  BNT162b2 doses given ~21 d apart.

Clinical Trial Protocol including Amendments Nos. 01 to 09 BNT162-01 Page 109 of 113 Version: 13.0 Date: 12 JAN 2022

The expansion cohorts implemented by this amendment are intended to provide a more indepth characterization of the adaptive immune responses induced by BNT162b2, associated vaccine safety, and the impact of factors such as subject disposition and dosing posology on humoral and cell-mediated immunity. These cohorts will extend the safety data of BNT162b2 to a broader trial population and thus closer to the vaccine target population.

For further background on the scientific rationale for the expansion cohorts, see Section 4.2.

The planned dose of BNT162b2, two 30 µg BNT162b2 doses given ~21 d apart, the same regime that has already been tested in the dose escalation phase of this trial and in almost 17,000 adult subjects, including those with acute and chronic illnesses, in the ongoing global Phase I/II/III trial BNT162-02/C4591001 (NCT04368728).

The three expansion cohorts are as follows:

- Cohort 11: Alternative posology cohort with 30 healthy adults who will receive BNT162b2 using one 3 µg prime dose and one 30 µg boost dose of BNT162b2 given approximately 21 d apart (P/B regimen).
- Cohort 12: Adaptive immune response cohort (including safety and long term immune response) with 90 healthy adults who will receive of two 30 µg BNT162b2 doses given approximately 21 d apart (P/B regimen).
- Cohort 13: Population expansion cohort (including safety and long term immune response) with 30 immunocompromised adults who will receive of two 30 µg BNT162b2 doses given approximately 21 d apart (P/B regimen).

This amendment also addresses feedback obtained from the PEI and the IEC on protocol version 8.0.

This amendment also introduces logistical simplifications, i.e., except for Cohorts 1 and 8, the minimum interval between dosed trial subjects has been reduced from 30 min to 15 min for the prime and boost doses in the still to be completed Cohorts 2 to 10 (inclusive). Also, the minimum interval has been set to at least 5 min for the prime and boost doses in Cohorts 11 and 12, and to 15 min (prime) and 5 min (boost for Cohort 13. This simplification/design is considered justified:

Because all FIH cohorts for the different BNT162 vaccine variants have been completed.

BioNTech SE	Clinical Trial Protocol	Page 110 of 113
	including Amendments Nos. 01 to 09	Version: 13.0
Confidential	BNT162-01	Date: 12 JAN 2022

• Due to the extensive experience and exposure already achieved with BNT162 vaccine candidates, including that almost 17,000 trial subjects have been dosed at least once with BNT162b2 (see Table 10).

Further changes were implemented to align data collection and reporting in this trial with the data collection and reporting in other trials with BNT162 vaccines candidates (to facilitate data merging).

This amendment will be issued after some of the planned trial subjects have already been enrolled into the trial.

# 10.10.7 Protocol amendment no. 06 (protocol version 10.0)

#### Update rationale

As requested by the IEC, this update reverses the reductions of the intervals between the dosing of trial subjects implemented in protocol amendment no. 06 (protocol version 9.0) for Cohorts 1 to 10 and Cohort 13.

This update will be issued after some of the planned trial subjects have already been enrolled into the trial.

# 10.10.8 Protocol amendment no. 07 (protocol version 11.0)

#### Update rationale

This update implements: a change in the sponsor name; deletion of the subject wellbeing calls given the available clinical data for BNT162b2; added text to avoid under reporting of mild COVID-19 related events arising in the trial; addition of a blood draw for CD4+ T-cell counting; removal of outdated content; correction of some errors; updates for clarification; updates of outdated data.

This update will be issued after some of the planned trial subjects have already been enrolled into the trial.

# 10.10.9 Protocol amendment no. 08 (protocol version 12.0)

#### Update rationale

This update implements one additional independent cohort (Cohort 14) comprising an additional 20 trial subjects receiving BNT162b2. Biomarker data from Cohort 14 are intended to provide characterization of B cell and plasma cell immune responses induced by BNT162b2, and to allow assessment of the durability of responses induced by vaccination in addition to continued follow-up of vaccine safety.

There is also a change to concomitant medication reporting to allow capture of vaccinations, e.g., SARS-CoV-2 vaccinations.

# 10.10.10 Protocol amendment no. 09 (protocol version 13.0)

#### Update rationale

This update implements changes to the follow-up visits of subjects in Cohorts 11 to 13 who receive non-trial SARS-CoV-2 vaccinations. For these subjects, blood samples for immunogenicity and cell-mediated immune testing will not be collected, and they will be discontinued from the BNT162-01 trial.

# **10.11** Data collection and management

The trial documentation must be adequate for the reconstruction of the trial.

# 10.11.1 Case report forms

The CRFs will be completed through use of an electronic data capture (EDC) system. Trial site personnel will receive training and have access to a manual for appropriate CRF completion. The CRFs will be submitted electronically to the sponsor via the system and should be handled in accordance with instructions from the sponsor.

All CRFs should be completed by designated, trained trial site personnel. CRFs should be reviewed, verified, and then electronically signed and dated by the investigator or a designee.

At the end of the trial, the investigator will receive trial subject data for his/her trial site in a readable format that must be kept with the trial records. Acknowledgment of receipt of the trial subject data will be required.

# 10.11.2 Trial subject reported outcomes

Not applicable.

# 10.11.3 Data management

The CRO (see the title page) will be responsible for data management of this trial, including quality checking of the data.

Data entered manually will be submitted to the sponsor through use of an EDC system, data extracts and reports. Trial sites will be responsible for data entry into the EDC system. In the event of discrepant data, the data management service provider will request data clarification from the trial sites, which the trial sites will resolve electronically in the EDC system.

The data management service provider will produce a Trial Data Validation Specification document that describes the quality checking to be performed on the data. CRFs and correction documentation will be maintained in the EDC system's audit trail.

Central laboratory data will be sent directly to the data management service provider.

System backups for data stored by the sponsor and records retention for the trial data will be in accordance with regulatory requirements.

Clinical Trial Protocol including Amendments Nos. 01 to 09 BNT162-01 Page 112 of 113 Version: 13.0 Date: 12 JAN 2022

# 10.11.4 Investigator's Site File and the Trial Master File

The principal investigator or deputy is responsible for the filing of all essential documents in an ISF. The sponsor is responsible for the timely filing of all essential documents in the TMF. As applicable, these files must be available at monitoring visits and during audits or regulatory inspections.

After trial completion, the principal investigator or deputy must ensure that all source data and documentation related to the trial is recorded, handled, and stored in a way that allows its accurate reporting, interpretation, and verification. The principal investigator or deputy must take measures to prevent accidental or premature destruction of these documents.

The principal investigator or deputy must keep the ISF, the source data/documentation arising from the trial according to the prescribed record retention period in the country and/or according to the hospital policy, but at least until informed by the sponsor that the trial-related records are no longer required.

# 10.12 Other data

# 10.12.1 Demographic data

At screening, the following demographic data will be recorded for all trial subjects:

- Age (in years/months)
- Gender (male/female)
- Ethnic group

# 10.12.2 Medical history

Medical history information will be recorded for at the times given in the SoA (Section 1.3).

# **Version History**

Table 1 SAP Version History Summary

SAP Version	Approval Date	Change	Rationale
1	08JUN2020	Not Applicable	Original version
2	04SEP2020	
 
BNT162c2 also P/B
 
Additional time points to evaluate endpoints
 
Older subjects included in the trial
 
	Adaptation to version 8 of the protocol
		

Analyses added for local and systemic reactions

Analyses added for TEAEs

	Additional analyses required
		

IMM set based on data of functional antibody titer

SD and Cis will only be calculated if data of at least

	Clarifications
		

3 subjects is available

Days since last immunization was harmonized with the rules for duration

	
		• Functional antibody titers with values below LLOD or above ULOD will not be imputed, as this is already implemented in the received SDTM data	
		• No overall tables will be created, as the tables will be created per vaccine	
		• Clarification of definition of concomitant medication	
		• Analysis of local and systemic reactions only based on data assessed in the diary	
		• Local and systemic reactions: denominator changed in the tables	
		Clarification of definition of TEAEs	
		• Change in interval of the TEAE analysis	
		• Denominator changed in analysis of seroconversion	

		• Change in reporting convention for functional antibody response	
3	16NOV2020	
 
Expansion cohorts
 
Part B will no longer be conducted
 
Changed wording: 'dose level' to 'cohort'
 
Specification of analysis of older subjects
 
	Adaptation to version 10 of the protocol
		
 
Listing for completers sets added
 
Analyses added for local and systemic reactions
 
New functional antibody responses
 
	Additional analyses required
		• Clarification of AE table by worst severity	Clarification
4	18NOV2020	

Changed 'elderly' to 'older'

Clarified definition of concomitant medication

	Clarification
5	13JUL2021	Inclusion of cohort 14	Adaption to protocol version 12
		Analyses based on completers sets were deleted	Analysis was planned for snapshots with cut-off before V7
		Deleted 'Major protocol deviations are those that are considered to have a significant effect on the treatment efficacy'	Updated to be more consistent with ICH E6 E3 R2 definition of important protocol deviations
		Minor changes/clarifications of tables, listings and figures	Analysis is more adequate.
		Only local and systemic reactions assessed by subject as in the diary will be analysed as primary endpoint. As additional analyses, the local and	Reactions assessed by the

		systemic reactions assessed by the investigator will also be included in tables displaying "worst possible grade" for data completeness.	investigator should also be included in the analysis.
		-TEAEs occurring in the time intervals including 7 days after each immunization will not be analyzed separately	Updated AE analysis
		- related TEAEs after 28 days after last dose are included in one of the analyzed time intervals	
		-TEAEs with DLT and deaths will be analyzed	
		- Removal of solicited reacto TEAEs that came from diary from the unsolicited TEAEs	
		Table of laboratory data by grades will only be done for lymphocytes	The table will be most useful for lymphocytes.
		References to mock tables were removed	
6	18AUG2021	Change in local and systemic reaction table	Updated reactogenicity analysis
		Clarification on assignment of Aes to time intervals and on the baseline definition	Clarifications
7	11APR2022	Update to protocol version 13.0.	New protocol version
		Data assessed after the vaccination with a non-trial SARS-CoV-2 vaccine will be excluded from all statistical analyses.	Adaptation to ongoing COVID-19 pandemic
8	01SEP2022	Added AE table	Additional table necessary for report
		Clarification on exclusion of data assessed after the vaccination with a non-trial vaccine	Clarification
9	110CT2022	Corrected numbering of section 1.3	Correction

## 1. Introduction

This document presents the statistical analysis plan (SAP) for BNT162-01, a dose-escalation phase I/II study in healthy and immunocompromised subjects. The results of this study might be included in a regulatory submission.

This SAP describes the detailed procedures for the planned statistical analyses for protocol version 13.0, dated 12 January 2022 (hereinafter referred to as "the protocol"). Changes from the protocol are documented in Section 7.1 Appendix 1.

The study consists of two parts, Part A and B. All analyses of Part A except for exploratory endpoints are described in this SAP including the analysis of CRF and laboratory data. The exploratory endpoint analyses will be described in a separate biomarker SAP developed by BioNTech. Due to changes in the overall clinical development plan, Part B will no longer be conducted.

The statistical analyses described in this document will be conducted by Staburo GmbH using SAS® software version 9.4 or higher.

This study will evaluate safety, adverse events and immunogenicity assessments data.

## 1.1. Objectives and Endpoints

Objectives	Endpoints a
Primary	
To describe the safety and tolerability profiles of prophylactic BNT162 vaccines in healthy adults after single dose (SD; prime only) or prime/boost (P/B) immunization.	
 
Solicited local reactions at the injection site (pain, tenderness, erythema/redness, induration/swelling) recorded up to 7 days (d) after each immunization (trial days 8 and 29).
 
Solicited systemic reactions (nausea, vomiting, diarrhea, headache, fatigue, myalgia, arthralgia, chills, loss of appetite, malaise, and fever) recorded up to 7 d after each immunization (trial days 8 and 29).
 
Deviating from protocol version 13.0, the endpoint related to unsolicited treatment emergent adverse events (TEAE) will be:
 
The proportion of subjects with at least 1 unsolicited treatment emergent adverse event (TEAE):         
 
o For BNT162a1, BNT162b1, BNT162b2 and BNT162c2 (P/B):
 
Occurring after prime immunization up to boost immunization or 28 d after the prime immunization (whichever comes first) and 28 d after the boost immunization.
 
o For BNT162c2 (SD):
 
 
 

Table 2: Objectives and endpoints

	The proportion of subjects with at least 1 unsolicited TEAE
	occurring up to 28 d after the immunization.
Secondary	
To describe the immune response in healthy adults after SD or P/B immunization measured by a functional antibody titer, e.g., virus neutralization assay or an equivalent assay available by the time of trial conduct.	
 
For BNT162a1, BNT162b1, BNT162b2 and BNT162c2 (P/B): As compared to baseline at 7 and 21 d after prime immunization and at 7, 14b, 21, 28, 63, and 162 d after the boost immunization:
 
Functional antibody responses (titers).
 
Fold increase in functional antibody titers.
 
Number of subjects with seroconversion defined as a minimum of 4-fold increase of functional antibody titers as compared to baseline.
 
For BNT162c2 (SD):
 
As compared to baseline at 7, 21, 28, 42, 84, and 183 d after the prime immunization (trial days 8 to 184):
 
Functional antibody responses (titers).
 
Fold increase in functional antibody titers.
 
Number of subjects with seroconversion defined as a minimum of 4-fold increase of 184):
 
Functional antibody responses (titers).
 
Fold increase in functional antibody titers.
 
Number of subjects with seroconversion defined as a minimum of 4-fold increase of functional antibody titers.
 

	as compared to baseline.
Exploratory	
The exploratory endpoints are described in the protocol, section 1.1.	

a) The given days are approximate; the respective schedule of activities defines assessment windows.

b) Only cohorts starting prime dosing after approval of amendment 09.

1.2. Study D	Design
--------------	--------

Study Design	The present study is a multi-site, phase I/II, dose- escalation trial investigating the safety and immunogenicity of four prophylactic SARS-CoV-2 RNA vaccines against COVID-19 using different dosing regimens in healthy and immunocompromised adults. The dose-finding part (Part A) includes several dose cohorts (treatment groups) for each vaccine.
Study Population	Part A: Healthy and immunocompromised adults aged 18 to 85 years.
	A detailed description of the inclusion and exclusion criteria can be found in section 5.1 and 5.2 of the protocol.
Geographic Regions	Part A: Multiple sites in Germany
Investigational Medical Products	
 
Name: BNT162 vaccines - Anti-viral RNA vaccines for active immunization against COVID-19
 
Part A: Type: RNA-LNP vaccines utilizing different BioNTech RNA formats, i.e., uRNA (product code BNT162a1), modRNA (two variants, product codes BNT162b1 and BNT162b2) and saRNA (product code BNT162b1, BNT162b2) and saRNA (product code BNT162b1, BNT162b2 and BNT162c2 will be administered using a P/B regimen. The vaccine BNT162c2 will additionally be administered using an SD regimen.
 
Dose:
 

	The doses are detailed in the protocol Table 1, 2, 3 and 4. Dose frequency: One injection or two injections 21 days apart. Injection volumes will be up to 1.5 mL. Administration route: Intramuscular Trial subjects with the first-in-human immunization will be immunized using a sentinel dosing/subject staggering.
Treatment and Study Duration	In total, the planned trial duration for subjects is expected to be approximately 214 d for Cohorts 1 to 10, 760 d for Cohorts 11 to 13 and 214 d for Cohort 14.

	A trial subject in Cohort 11, 12, or 13 who receives a non- trial SARS-CoV-2 vaccination will be withdrawn from follow-up and discontinued from the BNT162-01 trial.
Planned Number of Subjects	For each vaccine, 12 subjects for each cohort are required in Part A for non – expansion cohorts. For the expansion cohorts, 30 subjects will be included in cohort 11, 90 subjects in cohort 12 and 30 subjects in cohort 13. 20 subjects will be included in cohort 14.
Randomization and Blinding	No randomization, open-label

## **1.3.** Schedule of Visits and Procedures

The schedule of visits and procedures can be found in the protocol in Table 6, 7, 8 and 9.

## 2. Statistical Hypotheses

In Part A, there is no formal statistical hypothesis under test.

## 3. Interim Analyses

In Part A, no formal interim statistical analysis will be performed. However, preliminary analyses based on all data collected until a pre-defined data cut-off date (snapshot analyses) may be performed for each cohort once subjects within a cohort will have been followed up for at least 7 days following the dose.

The final analysis will be performed once all subjects of one vaccine construct have completed Visit 7 'end of treatment' or later. If necessary, an analysis update will be performed once all subjects of one vaccine construct will have completed the last planned visit.

## **3.1. Data Monitoring Committee (DMC)**

In Part A, no DMC is planned.

There will be a Safety Review Committee (SRC). For details see protocol section 10.1.5.

# 4. Sample Size Determination

No formal sample size calculations have been performed.

For further details regarding the sample size calculations see protocol section 9.2.

## 5. Analysis Sets and Subgroups

#### 5.1. Analysis Sets

#### **Screened Set (SCR)**

The screened set is defined as all subjects who signed informed consent.

#### Safety Set (SAF)

The safety set is defined as all subjects who received at least one dose of Investigational Medicinal Product (IMP).

#### Safety Boost Set (SAFB)

The safety boost set is defined as all subjects who received two doses of IMP (prime and boost immunization).

Note: Subjects receiving BNT162c2 as SD will be excluded from the SAFB as they receive only a prime immunization according to protocol.

#### Immunogenicity Set (IMM)

The immunogenicity set is defined as all subjects who received at least one dose of IMP and have at least one post-baseline functional antibody titer immunogenicity assessment.

#### Immunogenicity per-protocol set (IMMPP)

The immunogenicity per-protocol set is defined as all subjects included in the immunogenicity set that have no major protocol deviations as determined by the clinician.

Note: In all analysis sets, subjects will be assigned to the groups (i.e. vaccine type and cohort) according to the actual treatment they received ("as treated").

## 5.2. **Protocol Deviations**

Protocol deviations are failures to adhere to the inclusion/exclusion criteria and protocol requirements and will be classified into major and minor protocol deviations. They will include, but are not limited to, protocol deviations from the site as well as process deviations tracked by the sponsor.

Major protocol deviations will be identified by medical review prior to database snapshot for main analysis.

The following criteria might be considered as major protocol deviations:

(1) Violation of major inclusion or exclusion criteria

(2) Assignment to incorrect vaccine/dose (i.e. actual vaccine/dose taken differs from the scheduled)

(3) Non-Compliance (e.g. only one vaccine was administered of P/B vaccines or no vaccine was administered)

(4) Intake of prohibited concomitant medication

It will be discussed whether the protocol deviations are related to COVID-19 or not.

Major protocol deviations will be presented in a listing. For each vaccine, the number and percentage of subjects with major protocol deviations will be summarized in total and by protocol deviation type and by cohort and cohort-total.

## 5.3. Subgroups

In Part A, no subgroup analysis is planned. But unless otherwise specified, additional totals for younger (18 to 55 years) and older (56 to 85 years) subjects may be given.

## 6. Statistical Analyses

## 6.1. General Considerations

The following described statistical analyses only refer to Part A of the study.

No formal statistical testing will be done.

Unless otherwise specified, analyses will be based on data pooled across all study sites.

Data assessed after the vaccination with a non-trial vaccine will be excluded from all statistical analyses.

Clarifications:

- Data assessed on the same day as the non-trial vaccination will remain in the analysis.
- If the date of non-trial vaccination is missing, but month and year information is available, data assessed after the last day of the respective month will be excluded from statistical analysis.

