- f) Clinical laboratory tests: (Chemistry) alkaline phosphatase, creatinine, ferritin, C-reactive protein, albumin, alanine aminotransferase, amylase, aspartate aminotransferase, gamma glutamyl transpeptidase, total bilirubin, blood urea nitrogen, glucose, lipase, sodium, potassium, calcium; (Hematology) hemoglobin, hematocrit, red blood cell count, white blood cell count and differential (neutrophils, lymphocytes, monocytes, eosinophils, basophils), platelet count. Only in women who are not WOCBP (to confirm postmenopausal status): follicle stimulating hormone at Visit 0.
- g) Viral screening for human immunodeficiency virus (HIV) 1 or 2, hepatitis B, hepatitis C.
- h) Flexibility for visit days: Visit 3 Day 8±1 d; Visit 4 Day 22±2 d; Visit 5 Day 29±3 d; Visit 5a Day 36±3 d; Visit 6 Day 43±4 d; Visit 7 Day 50±4 d; Visit 8 Day 85±7 d; Visit 9 Day 184±9 d; Visit 10 Day 365±14 d; Visit 11 Day 547±14 d; Visit 12 Day 730±14 d.
- i) Only for HIV-positive subjects (done locally).
- j) Visits 8 and 9, only IMP-related AEs and any SAEs. Visits 10, 11, and 12, only any SAEs except proven COVID-19 cases which have to be reported regardless on severity and relatedness to the trial drug until the last scheduled FU Visit as described in Section 10.3.1.9. For subjects who receive non-trial SARS-CoV-2 vaccinations, the AEs expected to be captured after these vaccinations are within the frame of post-marketing safety data reporting (see Section 8.3.1).
- k) Blood draw for anti-SARS-CoV-2 antibodies.
- I) For first immunization in Cohort 13, immunization with at least 30 min intervals between the primary immunizations and 30 min between the boost immunizations. For Cohorts 11 and 12, the interval between the trial subjects will be at least 15 min for the prime immunizations and at least 5 min for the boost immunizations.
- m) Oral swipe for SARS-CoV-2 testing either on Day -1 or at the Visit 1 on Day 1.
- n) The timing of the listed "research" blood draw days may be adapted (within the 200 mL maximum volume) if justified by the collected data. Leftover blood after completion of the immunogenicity assessments may be used for additional analyses as described in Section 8.7 (Genetics) and/or Section 8.8 (Biomarkers). For subjects who receive non-trial SARS-CoV-2 vaccinations, there will be no blood sampling for immunogenicity or cell-mediated immune testing in the FU Visits.

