# 4.4 End of treatment (EoT) and end of trial definition

A trial subject is considered to have completed the trial if they have completed all planned visits as listed in the SoA, including all follow-up visits (see Section 1.3).

The EoT is defined as the date the last subject completed the EoT Visit (for BNT162c2 given SD Visit 6, for all cohorts with P/B dosing Visit 7).

BioNTech SE Confidential	Clinical Trial Protocol	Page 58 of 113
	including Amendments Nos. 01 to 09	Version: 13.0
	BNT162-01	Date: 12 JAN 2022

The end of trial is defined as the date when the last subject completed the last planned visit given in the SoA (see Section 1.3). The trial may end earlier if there are no remaining subjects from Cohorts 11 to 13 for the 2-year follow-up period (see Table 8); subjects who receive non-trial SARS-CoV-2 vaccinations will be discontinued.

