#### 6.5 **Concomitant therapy**

Any medication or vaccine (including over-the-counter or prescription medicines, vitamins, and/or herbal supplements, or other specific categories of interest) that the trial subject receives during the trial, i.e., starting after Visit 0 and until the respective EoT Visit, must be recorded along with the:

- Reason for use
- Dates of administration including start and end dates
- Dosage information including dose and frequency

Record any vaccination, including SARS-CoV-2 vaccination, received after the EoT Visit until the last FU Visit in the CRF.

The sponsor's Medical Monitor should be contacted if there are any questions regarding concomitant or prior therapy.

Trial subjects must abstain from taking prescription or non-prescription drugs (including vitamins and dietary or herbal supplements), unless, in the opinion of the investigator and sponsor, the medication will not compromise their wellbeing, or could prevent, limit, or confound the protocol-specified assessments.

Trial subjects are required to agree to not be vaccinated during the trial, starting after Visit 0 and continuously until 28 d after receiving the last immunization (see the inclusion criterion 13).

Trial subjects who receive non-trial SARS-CoV-2 vaccinations will be discontinued from the BNT162-01 trial (see Section 7.2).

Nonsteroidal anti-inflammatory drugs (NSAIDs), e.g., paracetamol/acetaminophen at doses of up to 4 g/day is permitted for use any time during the trial. Other concomitant

DiaNTach CE	Clinical Trial Protocol	Page 65 of 113
BioNTech SE Confidential	including Amendments Nos. 01 to 09	Version: 13.0
	BNT162-01	Date: 12 JAN 2022

medication may be considered on a case by case basis by the investigator, if required after consultation with the sponsor's Medical Monitor.

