# 7.2 Trial subject discontinuation/withdrawal from the trial

A trial subject may withdraw from the trial at any time at his/her own request, or may be withdrawn at any time at the discretion of the investigator for safety, behavioral, compliance, or administrative reasons.

A trial subject in Cohort 11, 12, or 13 who receives a non-trial SARS-CoV-2 vaccination will be withdrawn from follow-up and discontinued from the BNT162-01 trial.

If the trial subject withdraws consent for data processing, the sponsor may retain and continue to use any data collected before such a withdrawal of consent.

If a trial subject withdraws from the trial, he/she may request destruction of any samples taken and not tested, and the investigator must document sample destruction in the Investigator's Site File (ISF).

If the trial subject withdraws consent or is permanently discontinued from the trial, the trial subject will be permanently discontinued both from IMP administration and from the trial at that time.

BioNTech SE	Clinical Trial Protocol	Page 69 of 113
Confidential	including Amendments Nos. 01 to 09	Version: 13.0
	BNT162-01	Date: 12 JAN 2022

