# 8.3.1 Time period and frequency for collecting AE and SAE information

For Cohorts 1 to 10, all AEs and SAEs will be collected from the date of subject consent until discharge from the trial only IMP-related AEs and any SAEs will be collected.

For Cohorts 11 to 13 and 14, all AEs and SAEs will be collected from the date of subject consent until Visit 7 (the EoT Visit). From Visit 7 through 9 only IMP-related AEs, SAEs, and SARS-CoV-2 infections will be collected. After Visit 9 (e.g., Visits 10, 11, and 12) until the last scheduled FU Visit (i.e., when the subject is discharged from the trial), any SARS-CoV-2 infections and SAEs will be collected.

For subjects in Cohorts 11 to 13 who receive a non-trial SARS-CoV-2 vaccination, AEs/SAEs will be collected as specified above until the date when the subject was vaccinated with the non-trial SARS-CoV-2 vaccine. The AEs expected to be captured after non-trial SARS-CoV-2 vaccination are within the frame of post-marketing safety data reporting.

All SAEs (initial and follow-up reports) will be recorded and reported to the sponsor or designee within 24 h after becoming aware of the event, as indicated in Section 10.3.1.10.

Investigators are not obligated to actively seek AEs or SAEs after conclusion of the trial participation. However, if the investigator learns of any SAE, including a death, at any time after a trial subject has been discharged from the trial, and he/she considers the event to be reasonably related to the IMP administration or trial participation, the investigator must promptly notify the sponsor.

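### SAP 6.1 excludes data after any non-trial vaccine, while the protocol and SAP 1.2 name only SARS-CoV-2 vaccines; read literally, an unrelated vaccination removes valid late titers and adverse events

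*SAP*

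**What the plan says.** The exclusion rule is in SAP 6.1: "Data assessed after the vaccination with a non-trial vaccine will be excluded from all statistical analyses". Two clarifications follow. One keeps same-day data: "Data assessed on the same day as the non-trial vaccination will remain in the analysis". The other handles a vaccination date known only to month and year. Neither limits the type of vaccine.

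Every consequence stated elsewhere is limited to SARS-CoV-2 vaccines:

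- Sampling (Protocol 1.3, Table 8, footnote n): "For subjects who receive non-trial SARS-CoV-2 vaccinations, there will be no blood sampling for immunogenicity or cell-mediated immune testing in the FU Visits".
- End of trial (Protocol 4.4): "subjects who receive non-trial SARS-CoV-2 vaccinations will be discontinued".
- Withdrawal (Protocol 7.2): "A trial subject in Cohort 11, 12, or 13 who receives a non-trial SARS-CoV-2 vaccination will be withdrawn from follow-up". SAP 1.2 repeats this rule with the same qualifier.
- Safety collection (Protocol 8.3.1): "For subjects in Cohorts 11 to 13 who receive a non-trial SARS-CoV-2 vaccination, AEs/SAEs will be collected as specified above until the date" of that vaccination.

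Other vaccines are treated differently. Inclusion criterion 13 (Protocol 5.1.1) bars vaccination only until 28 days after the last immunization. After that, Protocol 6.5 asks sites to "Record any vaccination, including SARS-CoV-2 vaccination, received after the EoT Visit", up to the last follow-up visit. Nothing in the protocol stops sampling or AE collection after an unrelated vaccine.

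**The concern.** A subject who receives, say, an influenza vaccine in follow-up stays in the trial, is bled and has AEs collected. The rule as written then takes those valid data out of the tables.

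Two groups of results are exposed:

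- **Immunogenicity (SAP 6.5 to 6.5.3).** Late titers, fold rises and seroconversion are affected. Long-term monitoring of the immune response is a stated purpose of Cohorts 11 to 13 (Protocol 4.2), and these cohorts have the most late visits.
- **Late safety (SAP 6.4.3).** This covers related TEAEs through Visit 10 and the table of AEs after day 28, which includes SAEs, deaths and confirmed COVID-19 cases. Protocol 10.3.1.9 requires proven COVID-19 to be reported up to the last follow-up visit, yet a case after an unrelated shot would be missing from the table. SAP 6.1.1 keeps the full analysis set as denominator unless stated otherwise, and SAP 6.4.3 states nothing different for these tables. The percentages would therefore fall.

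Two programmers could also apply the rule differently, one to all vaccines and one to SARS-CoV-2 vaccines only.

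**Working it through.** The plan gives no figure of its own to reproduce. The check compares the texts (above) and then counts what the literal rule can remove. All days are nominal schedule days.

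**When an unrelated vaccine becomes permissible (criterion 13).**

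- Boosted on Day 22: 22 + 28 = Day 50, so from Day 51.
- Single dose, or boost withheld: 1 + 28 = Day 29, so from Day 30.

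Withheld boosts did occur: Protocol Table 1, note b (six subjects in Cohort 1A) and the notes to Table 2 (BNT162b1 at 60 µg). The notes to Tables 6 and 8 keep such subjects on the full schedule, and the note to Table 9 asks them to complete it.

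**Post-baseline titer visits that can be lost.** The maximum is the number of visits after the first permissible day. The minimum is 0, because a vaccination on or after the last visit costs nothing (same-day data stay in).

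| Schedule | Post-baseline titer days | Full dosing | Boost withheld |
|---|---|---|---|
| Table 6, P/B Cohorts 1–10 | 8, 22, 29, 36, 43, 50, 85, 184 | 0–2 of 8 | up to 5 of 8 |
| Table 6 without Visit 5a (Day 36) | 8, 22, 29, 43, 50, 85, 184 | 0–2 of 7 | up to 4 of 7 |
| Table 7, BNT162c2 SD | 8, 22, 29, 43, 85, 184 | 0–3 of 6 | not applicable |
| Table 8, Cohorts 11–13 | 8, 22, 29, 36, 43, 50, 85, 184, 365, 547, 730 | 0–5 of 11 | up to 8 of 11 |
| Table 9, Cohort 14 | 8, 15, 22, 29, 50, 184 | 0–1 of 6 | up to 2 of 6 |

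With the SARS-CoV-2 qualifier, an unrelated vaccine removes none of these visits.

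**Late AE percentages.** If a subject's only late AE follows the shot, the numerator falls by 1 and N stays the same, so the shift is 100/N percentage points:

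- N = 12 (dose-ranging cohort): 100/12 = 8.3
- N = 20 (Cohort 14): 100/20 = 5.0
- N = 30 (Cohorts 11 and 13): 100/30 = 3.3
- N = 90 (Cohort 12): 100/90 = 1.1

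**Precision of a late geometric mean titer.** If one of 12 titers is lost and the SD on the log scale is unchanged (assumed), the 95% CI half-width grows by √(12/11) × 2.228/2.201 = 1.057, about 6%.

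**Primary windows.** Solicited reactions end 7 days after each dose. The unsolicited TEAE window ends 28 days after the last dose, including for subjects without a boost (SAP 6.4.3). Criterion 13 bars vaccination throughout both, so a compliant subject loses nothing there.

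**The case against.** The best defence is that the meaning can be recovered. Elsewhere in the operative text, *non-trial* qualifies only SARS-CoV-2 vaccination. The SAP version history, which is context only, describes the exclusion at version 7 with the qualifier and calls the version 8 change a clarification. That makes shorthand the likely explanation, and it limits the severity. It does not settle the matter, because analyses are programmed from SAP 6.1 and that section does not say it.

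A second defence is that a wide rule could be intended. The protocol bars all vaccines, not only SARS-CoV-2 vaccines, before and shortly after dosing. But the SAP gives no reason for a wide rule. SAP 1 says changes from the protocol are recorded in SAP 7.1, and no such exclusion is listed there.

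Third, the trial is descriptive, and SAP 6.4.3 and 6.5 also plan listings of AEs, titers, fold rises and seroconversion, so a reader may still find the data. That stands, but the summary tables would be incomplete.

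Some inferences go too far in either direction:

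- A reader might infer that the primary safety results are compromised. They are not, if criterion 13 is followed.
- A reader might infer that SAP 6.1 breaks a protocol analysis rule or, conversely, that for SARS-CoV-2 vaccines in Cohorts 11 to 13 it merely carries one out. The protocol has no rule excluding data from analysis; it only stops sampling and collection. Protocol 7.2 also asks subjects discontinued after EoT to complete the last-visit assessments if possible, so some data after such a vaccination may exist.
- A reader might see a conflict in Protocol 6.5, which discontinues vaccinated subjects without naming cohorts. It refers to Section 7.2, which names Cohorts 11 to 13.

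**Conclusion.** The rule is wrong as written: followed literally, it discards valid late data for a reason neither document supports. Severity is minor to should-fix, because the intended meaning is probable and the primary windows are protected.

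The per-subject effects are those worked out above. They assume nominal visit days, compliance with criterion 13 and, for the percentage shift, a subject whose only late AE comes after the shot. The documents do not say how many subjects received an unrelated vaccine, so the realised effect on any table is unknown and could be zero. A claim that the late results are materially distorted would not be supported.

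**What to change.** In SAP 6.1, replace *non-trial vaccine* and *non-trial vaccination* with *non-trial SARS-CoV-2 vaccine* and *non-trial SARS-CoV-2 vaccination* in the rule and in both clarifications. List the exclusion in SAP 7.1, since the protocol contains no rule that removes data from analysis. If the sponsor does mean every vaccine, SAP 6.1 should say so and give the reason, again with an entry in SAP 7.1.

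The cost is three edited sentences and one added entry. No new data, tables or analyses are needed.
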